Title: Towards understanding the relationship between meals and blood biomarkers

Date: 12/22/2021

PI [name]

Collaborators [name], [name], [name], [name], [name], [name]

Significance

The long-term objective of this project is to create a counterfactual-based lifestyle intervention that curtails the progression of prediabetes to T2DM through management and knowledge of food choices. This is a significant objective since 70% of prediabetes patients go on to develop T2DM. The project addresses a major objective of PATHS-UP in general and Thrust 4 in particular, by developing an innovative behavior-change intervention that will eventually make use of information from the Lab-on-your-Wrist device.

Innovation

To our knowledge, this is the first project to (1) propose an intervention based on counterfactual thinking for diabetes prevention and (2) combine continuous glucose monitors (CGMs) and food photography to promote a better understanding of how food choices affect blood glucose.

Specific Aim

The specific aim of this project is to establish the validity of leveraging photo-based food diaries and CGMs to engage counterfactual thinking strategies that improve food choices amongst prediabetes participants. This will be measured by changes in (1) eating attitudes and behaviors, (2) behavioral intentions to improve healthy eating behavior, (3) motivation to improve eating behavior, (4) increased self- efficacy for healthy eating, and (5) number of glucose excursions and time-in-range.

Approach

Study design: We will recruit up to 40 subjects diagnosed with Type 2 diabetes and prescribe glucose-lowering medication(s). Informed consent will be obtained on the screening day before any study related procedures will be performed. Blood will be sampled through venipuncture technique on the upper arm. A blood sample of 4 mL will be collected for each measurement of the subject's A1c. A total of 8 mL will be collected for the whole study, one on the screening visit and one on the last study day. If inclusion/exclusion criteria are met, subjects are invited to take part in the study. The study involves 1 screening visit lasting up to 2 hours and fasting prior to screening is required. We will screen the subjects for any disease or condition that could interfere with the studies and complete study related questionnaires.

On the first study day, we will place the Freestyle Libre Pro and continue monitoring for 2 weeks. Subjects will also complete baseline behavioral measures/dietary habit questionnaires. During this time, participants will be asked to take at least 3 photographs of their meals and send them to the researchers via text-messaging using MyCAP. Communication with participants via MyCAP will be done to confirm receipt of photos (e.g., "Good job with the photos yesterday, keep it up today!"), reminders if photos are missed (e.g., "It seems you sent fewer photos yesterday than your survey indicates meals you eat. If you missed a picture yesterday, remember to try and take photographs of all food today."), or tips to improve photos for image analysis (e.g., "Good job with the photos yesterday, but please try to adjust lighting/focus to properly capture all food.").

The subject will return after continuous wearing of the CGM monitor and sending of photos after the 2 weeks. At this second study day the CGM will be replaced and all data on the old CGM will be downloaded by the

researchers. The subject will then wear the new CGM monitor and continue to send pictures of all meals for 1 week before returning for their third visit.

At the third visit, a new CGM will be placed and the subject will be randomized into behavioral intervention.

1. One intervention will be based on counterfactual thinking, which will allow the subjects to think of an alternative reality that “might have been” based on the concurrency of their glucose readings and the meals they ate.
2. The control condition will use reflective writing. These subjects will be engaged in reflective writing intervention. They will look at your CGM readings throughout the first two weeks and compare them to the food eaten at those specific times. They will then be asked to reflect on the meals and how they feel about the changes in glucose levels based on the food choices made.

After this visit, they will then continue to wear the CGM monitor and take photos of their meals. They will return for their fourth visit in 2 weeks.

The fourth visit will consist of permanently removing the CGM monitor and conducting post-treatment interviews and behavioral measures/dietary habits with the subjects.

Subjects will return for their fifth and sixth follow-up visit 2 months post intervention. At each of these visits their A1c will be measured through a blood collection of 4 mL by venipuncture. Delayed post-test interviews, and behavioral measures/dietary habits will also be conducted.

Description of the CBLI intervention

In the CBLI, participants will be shown healthy (low PPGR) and unhealthy (high PPGR) samples of their food photographs with the corresponding glucose responses (see Data Synchronization & Meal Selection & Figure 1b). For counterfactuals to be an effective self-regulatory tool, one needs information from a personal negative experience relevant to the current goal. Using healthy and unhealthy meal selections and their resulting CGM responses will make the causal relationship between food choices and glucose response more salient, and will increase the effectiveness of the counterfactual intervention, in which they generate ways they could have changed their food choices and subsequently improved the CGM response. Participants will be asked to compare the healthy and unhealthy meals and generate counterfactuals about how they could have altered the unhealthy meal (e.g., replace white bread with a tortilla) such that it would have improved the outcome (i.e., lower glucose responses). To increase the likelihood of participants generating accurate counterfactuals that could have improved their PPGR outcome, participants will be provided lists of effective eating strategies to aid their counterfactual generation. Afterwards, participants will evaluate each counterfactual thought and list at least one situation in the near future in which they could implement the eating behavior described in the counterfactual, and describe any barriers they imagine could reduce the likelihood of implementing the behavior. Our expectation is that the counterfactual thoughts generated during the intervention will lead to better food choices and increased motivation in the weeks that follow.

This session will be video recorded to ensure treatment fidelity and code participant responses.

Behavioral measures/dietary habit Questionnaires

General Health Intentions. Designed to collect ratings of intentions to engage in healthier food habits over the next six months.

Motivation. The Regulation of Eating Behaviors Scale is designed to measure subject motivations for eating including to cope with negative affect, to be social, to comply with others' expectations, and to enhance pleasure.

Self-efficacy & Self-Regulation. Measured by the 5-item Eating Self-efficacy Scale and the Self-regulation of Eating Behavior Questionnaire.

Behavioral Intentions. Three items designed based on the Theory of Planned Behavior to measure intention to eat healthy using counterfactual strategies developed in Study Visit #3 (intervention group only).

Inclusion criteria

- Ability to walk, sit down and stand up independently
- Diagnosed with type 2 diabetes (T2D) and take glucose-lowering medication(s).
- Motivated to learn how to regulate blood glucose through non-medical intervention such as changes to eating behavior
- Subject is judged to be in satisfactory health based on medical history, physical examination
- Willingness and ability to comply with the protocol
 - Use your smartphone to upload pictures of meals through MyCap

Exclusion criteria

- Subject has planned elective surgery requiring 2 or more days of hospitalization during the entire study
- Allergy to adhesives
- Planned medical procedures that are documented to interfere with CGM readings, such as
 - Xylose absorption testing (oral sugar testing)
 - CT
 - MRI
 - X-ray
 - Diathermy treatment (high-frequency electric current to stimulate heat generation within body tissues)
- Established diagnosis of malignancy
- Presence of acute illness or metabolically unstable chronic illness
- Any other condition according to the PI, nurse, or study coordinator that was found during the screening visit, that would interfere with the study or safety of the patient
- Failure to give informed consent or Investigator's uncertainty about the willingness or ability of the subject to comply with the protocol requirements

When during the period from enrollment to completion of the study any condition is developed, whether causing the subject to not meet inclusion criteria or to meet exclusion criteria, the subject will be excluded from the study. Family history of type 2 diabetes will be used only for post-stratification of those who can report.

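### The Specific Aim is about people with prediabetes, but only people already diagnosed with type 2 diabetes can enter the trial

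*Protocol*

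**What the plan says.** The Specific Aim is to show that photo-based food diaries and continuous glucose monitors (CGMs) can be used to "engage counterfactual thinking strategies that improve food choices amongst prediabetes participants". It continues: "This will be measured by changes in (1) eating attitudes and behaviors", and goes on to list intentions, motivation, self-efficacy and CGM-based glucose measures, five groups in all.

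The text before the aim points the same way. Significance gives a long-term objective of an intervention that "curtails the progression of prediabetes to T2DM through management and knowledge of food choices". Innovation claims to be the first to "propose an intervention based on counterfactual thinking for diabetes prevention".

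The text that decides who enters the trial says something else. Under Approach, the Study design paragraph reads: "We will recruit up to 40 subjects diagnosed with Type 2 diabetes and prescribe glucose-lowering medication(s"). The inclusion criterion reads: "Diagnosed with type 2 diabetes (T2D) and take glucose-lowering medication(s").

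**The concern.** The aim and the eligibility text name different populations. Significance itself treats prediabetes as the state that comes before type 2 diabetes, so a person who meets the inclusion criterion has already left the population named in the aim.

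At stake is what the trial may claim. The aim sets the conclusion a reader will expect, and that conclusion would be about prediabetes. The problem is sharpest for the glucose outcomes: excursions and time-in-range would be observed in people with established disease who take glucose-lowering drugs, so they do not directly answer a question about people with prediabetes. Nor can prevention of diabetes be assessed in people who already have it.

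**Working it through.** No arithmetic beyond counting applies, and the Protocol gives no figure to reproduce on this point. The check sets the texts side by side and looks for anything that would reconcile them.

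| Place in the Protocol | Population or purpose named |
|---|---|
| Significance | Prediabetes, before progression (long-term objective) |
| Innovation | Diabetes prevention |
| Specific Aim | Prediabetes participants |
| Approach, Study design | Diagnosed type 2 diabetes with glucose-lowering medication, up to 40 |
| Inclusion criteria | Diagnosed type 2 diabetes, taking glucose-lowering medication |

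1. **Is the aim about this study?** Yes. Its second sentence says how it will be measured, and the five outcome groups listed are measures of this study's own participants.

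2. **Is there another way in for prediabetes?** No. There are 5 top-level inclusion criteria (mobility, diagnosis with medication, motivation, satisfactory health, compliance). There are 7 top-level exclusion criteria (elective surgery, adhesive allergy, procedures that interfere with the CGM, malignancy, acute or unstable illness, other conditions, consent or compliance). Only the diagnosis criterion sets a diabetes status. The inclusion list offers no alternatives and no qualifying A1c range. Anyone who stops meeting a criterion during the study is to be excluded, so the requirement applies throughout.

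3. **Is the difference explained anywhere?** No. The word prediabetes occurs 3 times, twice in Significance and once in the Specific Aim, and never from the Approach onward. No text says that people with type 2 diabetes stand in for people with prediabetes, or argues that findings carry over from one group to the other.

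4. **Result.** Eligible participants who belong to the population in the aim: 0 of up to 40. All five outcome groups are measured in a population other than the one the aim names.

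**The case against.** The best reply is that the text which governs enrolment is consistent. Study design and the inclusion criterion agree, so no site would be unsure whom to recruit. The prediabetes wording can be read as carried over from the wider programme: Significance speaks of a long-term objective and of a device to be used eventually. On that reading the defect is two words in framing text, with an editorial remedy, and the eligibility counts merely restate one criterion.

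Part of this stands. Recruitment is not ambiguous, and everything in the counts does follow from a single criterion. The programme reading is a fair account of Significance, which may stay as a long-term objective. It does not rescue the Specific Aim, which speaks of participants and ties them to outcomes measured here. This is also not a detail that could be left to a statistical analysis plan: the aim and the eligibility criteria belong to the Protocol, both are present, and they disagree.

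A further caution is fair. The Protocol states no power, effect size or standard deviation, so no effect on power can be checked. The between-arm comparison can be called unaffected only while eligibility stays as written.

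**Conclusion.** The concern holds. The only stated aim names a population that the eligibility criteria shut out completely: 0 of up to 40 participants can belong to it. With eligibility as written, randomisation and measurement stand and the comparison between arms is valid for the people enrolled; the error lies in the population to which the result is attached. It should be corrected before the trial is reported.

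This rests on reading prediabetes and diagnosed type 2 diabetes as distinct states, as the Protocol itself does when it speaks of progression from one to the other. Two agreeing eligibility texts make type 2 diabetes the likelier intention, but the Protocol does not settle which population was meant.

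**What to change.** Reconcile the Specific Aim, the Study design paragraph and the inclusion criteria so that they name one population. The choice is the sponsor's.

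- **If type 2 diabetes is intended:** restate the aim as concerning participants diagnosed with type 2 diabetes, and limit the conclusion to them. Align the prevention wording under Innovation. Significance may keep prediabetes as the long-term objective, preferably with a sentence that describes this study as a step towards it and says why findings might carry over. The cost is wording only; recruitment, visits, randomisation and measurements do not change. The downside is that the result cannot be reported as evidence in prediabetes.
- **If prediabetes is intended:** change the Study design sentence and the inclusion criterion. That means recruiting a different population. The variability of the glucose outcomes and the effect on them could then differ, so any sample-size reasoning held elsewhere would need to be looked at again.

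### Does counting glucose excursions over unequal CGM periods, with no stated time base, distort the glucose outcome?

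*Protocol*

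**What the plan says.** The Specific Aim introduces its outcomes as changes ("This will be measured by changes in (1) eating attitudes and behaviors") and ends the list with "5) number of glucose excursions and time-in-range". It does not say whether the excursion count is a total, a daily rate or something else.

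The Approach section sets the CGM schedule:

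- First study day: "we will place the Freestyle Libre Pro and continue monitoring for 2 weeks".
- Second study day: the sensor is replaced and participants "wear the new CGM monitor and continue to send pictures of all meals for 1 week before returning for their third visit".
- Third visit: a new sensor is placed and participants are randomised. After that, "They will return for their fourth visit in 2 weeks".
- End of monitoring: "The fourth visit will consist of permanently removing the CGM monitor".

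The only CGM window singled out is in the description of the control condition: "They will look at your CGM readings throughout the first two weeks". That describes material for the reflective-writing task and does not define a baseline for analysis.

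**The concern.** A number of excursions grows with the days observed. Monitoring lasts 21 days before randomisation and 14 after, and the 21 days come from one 14-day and one 7-day sensor. A reader who takes the outcome literally, as a change in a raw count, has three candidate baselines, and only the first sensor period matches the follow-up in length. With either of the others, the size and even the sign of the reported change would be set partly by the calendar.

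Three things would be at stake. A within-arm summary could show both groups improving by a third with no true effect. An unscaled change score against 21 days would also be noisier, which matters with at most 40 participants. Finally, a raw count rewards lost wear, because a sensor that comes off early records fewer excursions. Time-in-range taken as a proportion of readings has none of these problems.

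**Working it through.** **Inputs from the protocol.** Candidate baseline lengths d = 21, 14 or 7 days; follow-up 14 days; at most 40 participants; both arms on the same CGM schedule. The protocol gives no figure for excursion rates or their variability and no power calculation for this outcome, so there is no stated figure to reproduce.

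**Assumptions, not from the protocol.** Mean rate m = 1 to 3 excursions per day, between-person CV 0.3 to 0.5 (SD t = CV × m), Poisson counts within person, 20 per arm, full wear unless stated.

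**1. Null change in a raw count.** At a constant rate the expected change is 14/d - 1.

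| Baseline | Formula | Null change | Example at 2 per day |
|---|---|---|---|
| 21 days | 14/21 - 1 | -33.3% | 42 to 28 |
| 14 days | 14/14 - 1 | 0% | 28 to 28 |
| 7 days | 14/7 - 1 | +100% | 14 to 28 |

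A true 20% fall in rate gives 0.8 × 14/d - 1, that is -46.7%, -20% or +60%. Per day of wear, the null change is 0% for all three windows.

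**2. Does this reach the randomised comparison?** The shift is the same in both arms and cancels in their difference. A null simulation (1, 2 or 3 per day, gamma shape 4 between persons, 20 per arm, 20,000 runs per setting) gave:

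| Test on raw change | 21 days | 14 days | 7 days |
|---|---|---|---|
| Between arms, rejection rate | 4.8% to 5.0% | 5.0% to 5.2% | 4.9% to 5.2% |
| Within one arm, rejection rate | 99.8% to 100% | 4.9% to 5.1% | 100% |

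The mean between-arm difference was within 0.03 excursions of zero throughout. The artefact is confined to within-arm change.

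**3. Precision.** On the 14-day scale:

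- Var(raw change) = (14 - d)² t² + (14 + d) m
- Var(per-day change) = 14m + (14/d)² d m

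The ratio of the two is 1.5 + 2.1 t²/m for d = 21, 1.0 for d = 14, and 0.5 + 1.167 t²/m for d = 7. Since t²/m = CV² × m, it runs from 0.3² × 1 = 0.09 to 0.5² × 3 = 0.75. The ratio is therefore 1.69 to 3.08 (21 days), 1.00 (14 days) and 0.60 to 1.38 (7 days).

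Example with d = 21, m = 2, CV 0.5 (t = 1):

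- Raw change: variance 49 + 70 = 119; SE of the arm difference √(2 × 119/20) = 3.45.
- Per-day change: variance 28 + 18.67 = 46.67; SE √(2 × 46.67/20) = 2.16.
- ANCOVA: post variance 28 + 196 = 224, baseline variance 42 + 441 = 483, covariance 14 × 21 = 294; residual variance 224 - 294²/483 = 45.04; SE √(2 × 45.04/20) = 2.12.

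With full wear, ANCOVA gives the same SE whether the baseline enters as a 21-day count or as a daily rate, because rescaling a covariate only rescales its coefficient. The loss thus comes from the unscaled change score over 21 days and not from the missing time base as such.

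**4. Wear.** A sensor that records 10 of 14 days lowers the count by 1 - 10/14 = 28.6%. Each day of difference in mean wear between arms shifts the contrast by 1/14 = 7.1% of the count.

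**The case for a change.** The best case for a change is that the protocol itself chose the word number, framed it as a change and set unequal periods around randomisation, so the outcome is badly fixed and not merely unfinished. A matched 14-against-14 comparison is nowhere stated, and it would discard the week closest to randomisation. Under the assumptions above, an unscaled 21-day change score would leave 40 participants with the information of about 40/3.08 = 13 to 40/1.69 = 24. The repair would take one sentence and no new data.

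Some of this stands. The protocol names no CGM baseline, and because the aim speaks of changes, a careless within-arm summary is possible.

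The rest depends on steps the protocol does not take. The item is one line in an aims paragraph and does not prescribe subtracting unscaled totals. The precision loss needs three choices together: an unscaled count, the 21-day window and a simple change score. With the 7-day window the raw change can even be the more precise. The wear bias needs sensor loss that differs between arms. The protocol plans wear up to each visit and gives no reason to expect such a difference. Setting aside one week to obtain equal windows would be a fair trade-off, and daily rates avoid even that.

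**Conclusion.** The concern does not call for a change. The schedule and the figures of -33.3%, 0% and +100% are correct, but they describe a calculation the protocol does not specify. What is missing is a time base, a named window and a wear rule, which are commonly left to the statistical analysis plan. That plan was not available for this review and may supply them.

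Either obvious choice, excursions per day of valid wear or the first 14 days against the last 14, brings the null change to 0%. With equal wear the randomised comparison is unbiased whichever window is used, and ANCOVA loses no precision even on the unscaled count. Only a within-arm change in raw counts over unmatched windows, or unequal wear between arms, would mislead. The point touches half of one of five listed outcomes.

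The 14/d figures rest on a constant rate and full wear. The variance ratios, standard errors and rejection rates also rest on assumed rates, between-person variation and Poisson counts. If the authors revise the text for other reasons, stating the count per valid day, naming the pre-randomisation window and comparing arms after randomisation with adjustment for each participant's own earlier value would be a reasonable clarification, but it is optional.

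### As written, candidates on glucose-lowering drugs start a study-imposed fast before consent and before the described health screen

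*Protocol*

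**What the plan says.** The relevant rules are all in the Protocol.

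- **Fast and visit** (Approach, Study design): "The study involves 1 screening visit lasting up to 2 hours and fasting prior to screening is required". Neither the length of the fast nor the reason for it is given.
- **Consent** (same paragraph): "Informed consent will be obtained on the screening day before any study related procedures will be performed".
- **Health screen** (same paragraph, immediately after the fasting sentence): "We will screen the subjects for any disease or condition that could interfere with the studies and complete study related questionnaires".
- **Population** (Study design and Inclusion criteria): people with diagnosed type 2 diabetes who are being treated with drugs that lower glucose.
- **Health criteria**: the Inclusion criteria ask that "Subject is judged to be in satisfactory health based on medical history, physical examination". The Exclusion criteria list "Presence of acute illness or metabolically unstable chronic illness". A separate catch-all exclusion covers other conditions that come to light at the screening visit and bear on the study or on patient safety.
- **Blood tests**: the Study design paragraph describes venipuncture for A1c and names no other assay. For the follow-up visits, the paragraph before the description of the CBLI intervention says: "At each of these visits their A1c will be measured through a blood collection of 4 mL by venipuncture". It does not mention fasting.

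**The concern.** A person told to arrive fasted has begun doing something for the study before arriving. If consent is taken on arrival, the fast comes first. The people concerned are not healthy volunteers: the eligibility criteria require treated type 2 diabetes, so each eligible candidate is on a drug that lowers glucose while going without food. The text available says nothing about how that drug is to be handled during the fast.

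The health screen has the same problem of order. It exists partly to find people who should not take part for reasons of safety, and anyone it finds will already have fasted. What is at stake is participant protection and the protocol's consistency with its own consent rule. Estimates, error rates, power and randomization are not involved.

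**Working it through.** There is no stated figure to reproduce. The check concerns the order of three events: start of fast, consent and health screen.

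**Inputs.** One screening visit of at most 2 hours; fasting required before screening; consent on the screening day; disease screen at the visit (all from Study design). Treated type 2 diabetes (Study design and Inclusion criteria). Fast length: not given.

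**Step 1: fast against consent.** Let F be the length of the fast and G the time from consent to the first screening step that is meant to be done fasted. The fast starts after consent only if F ≤ G.

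- *Consent taken at the visit.* The whole visit lasts at most 2 hours, so G ≤ 2 hours. Any fast with F > 2 hours therefore starts before consent. The plain wording goes further: a fast to be kept before screening means arriving fasted, and that precedes an in-visit consent whatever F is.
- *Consent taken earlier on the screening day, outside the visit.* G may then exceed 2 hours, and the fast could follow consent. The text describes no such contact. Even then, a fast that runs through midnight starts on the previous day, ahead of any consent given on the screening day.

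On the natural reading, then, the fast comes before consent. The only reading that reverses the order needs an undescribed contact and a fast short enough to fit after it on the same day.

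**Step 2: fast against health screen.** The fast is required before screening, and the disease screen is part of screening. The fast therefore precedes the described health screen under either consent arrangement in Step 1.

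**Step 3: is there a measure that needs the fast?**

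| Blood draw described | Test | Fasting stated? |
|---|---|---|
| Screening | A1c | Yes, through the screening rule |
| Follow-up visits | A1c | No |

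The same test is drawn with a fast at screening and without a stated fast at follow-up, so the protocol does not itself treat A1c as needing one. The other screening content named is medical history, physical examination and questionnaires, and none of it is said to need a fast. Fasting measures named: 0.

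**Step 4: reach.** The rule applies to everyone who attends screening. The protocol plans to recruit up to 40; it does not state how many will be screened, so no firmer count is available.

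**The case against.** The strongest reply is that the consent rule concerns procedures that staff perform, such as venipuncture and examination, and that arriving without breakfast is not one of them. **This stands in part.** The protocol does not define the term, so a reader who infers a proven breach of the consent rule goes beyond the text. The order of events, and the missing medication guidance, remain whichever label is used.

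Second, the consent pages are not in the material available. They may give the length of the fast, tell candidates what to do with their medication, and show when candidates receive that advice. **This stands as a limit.** The point rests on the timing that the Study design paragraph states, not on the absence of consent wording.

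Third, a reader might infer that nobody checks metabolic stability before the fast. **The documents do not support that.** The exclusion for unstable illness does not say how or when it is ascertained; only the catch-all exclusion is tied to the screening visit. An earlier check by telephone or from records is neither described nor ruled out. What can be said is that the health screen the protocol does describe comes after the fast.

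Fourth, a reader might take 2 hours as a firm limit beyond which any fast must predate consent. **That holds only if consent is taken inside the visit.** The text says the screening day, which is slightly wider.

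Fifth, the case that the fast has no purpose is an argument from silence, since the protocol does not list every screening test. **This is fair**, and it is why deletion should depend on whether a fasting measure is intended.

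**Conclusion.** The point holds as a conflict between the protocol's own rules on fasting, consent and screening. It is a stated rule that is badly placed, not merely a missing detail. Two assumptions carry the consent part: that consent is taken at the visit, or too late that day for the fast to follow it, and that the fast is required of candidates because of the study. The health-screen part follows from the wording alone.

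Its reach is every candidate screened. Its clinical size cannot be stated: without fast length and drug classes there is no basis for a hypoglycaemia rate, and none should be inferred. There is no effect on outcome data. The change is worth making because it protects participants at little cost, but it is not a ground for doubting the trial's results.

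**What to change.** **If no fasting measure is intended:** delete the second half of the sentence that sets the screening visit, from the conjunction onward, so that it states only the number and length of visits. This is a one-clause amendment. It removes the fast, and with it both ordering problems.

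**If a fasting measure is intended:** name it and give the length of the fast. Change the Study design paragraph so that documented consent, for example remote, is obtained before the fast is instructed, and issue instructions on glucose-lowering medication together with the fasting instruction. The cost is one earlier contact per candidate. This route puts consent first but leaves the health screen after the fast, so the medication instructions are an essential part of it.

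Neither route alters any outcome measurement.

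### Do the strategy lists, selected meals and planning steps described only for the CBLI arm undermine the comparison with reflective writing?

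*Protocol*

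**What the plan says.** Participants are randomised at the third visit to one of two sessions. The Protocol, under Description of the CBLI intervention, sets out the CBLI session in detail. First, "participants will be shown healthy (low PPGR) and unhealthy (high PPGR) samples of their food photographs with the corresponding glucose responses". They then compare these meals and generate counterfactuals about the unhealthy one, and "participants will be provided lists of effective eating strategies to aid their counterfactual generation". Next they evaluate each counterfactual, "list at least one situation in the near future in which they could implement the eating behavior described in the counterfactual", and describe barriers. The section closes with the expectation that "counterfactual thoughts generated during the intervention will lead to better food choices" and to greater motivation.

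The control has only a few sentences under Approach. "They will look at your CGM readings throughout the first two weeks" and "compare them to the food eaten at those specific times"; they are then "asked to reflect on the meals and how they feel about the changes in glucose levels". Before the third visit all subjects wear a CGM for two weeks, after which they change the CGM and "continue to send pictures of all meals for 1 week before returning for their third visit".

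**The concern.** When two arms differ in several ingredients, the randomised difference belongs to all of them together. Here the expectation sentence credits one ingredient, the counterfactual thoughts. The strategy list is the awkward element: it is dietary advice, the protocol itself calls the strategies effective, and the inclusion criteria select people motivated to change how they eat. The list could improve food choices in someone who never forms a counterfactual. A better CBLI result on self-efficacy, motivation, general health intentions, glucose excursions or time-in-range might then be credited to counterfactual thinking when advice produced it. Coding the recorded sessions would not settle this, because evidence from it is not randomised.

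A second apparent mismatch is the review window. Controls look back over two weeks, although three weeks of data exist by the third visit.

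**Working it through.** The protocol gives no sample-size or power derivation to reproduce, and the main question is what the contrast can identify. So the two descriptions are set side by side.

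| Element | CBLI | Reflective writing |
|---|---|---|
| CGM wear and meal photographs | yes | yes |
| Own glucose reviewed against own meals | yes | yes |
| Selected low/high-response meals | described | not described |
| Counterfactuals generated and evaluated | described | not described |
| Eating-strategy lists | described | not described |
| Situation and barrier planning | described | not described |

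**What is identified.** The arm difference estimates the joint effect of the last four rows. No sample size separates one row from the others.

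**How separable the extra rows are.** The selected meals are the material that the counterfactuals are about. The planning step concerns the behaviour named in each counterfactual. Both read as parts of the counterfactual task. The list is also offered as an aid to that task, but it is the one element that could plainly act without it.

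**What the plan claims.** The Specific Aim concerns using food photographs and CGM data to engage counterfactual strategies, which is a combination. The long-term objective under Significance is a lifestyle intervention built on counterfactuals. Approach describes the arm as based on such thinking. All three fit a test of CBLI as a whole. Only the expectation sentence names the thoughts by themselves.

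**Size of a list-only effect (illustration).** Assumptions not in the protocol: the maximum of 40 split 1:1, so n = 20 per arm; a two-sided 5% t-test with 20 + 20 − 2 = 38 degrees of freedom; no effect of counterfactual thinking; and a list effect of d SD. The noncentrality is d × √(n/2) = d × √10.

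| d | Noncentrality | P(significant in favour of CBLI) |
|---|---|---|
| 0 | 0 | 2.5% |
| 0.2 | 0.632 | 9.0% |
| 0.3 | 0.949 | 15.0% |
| 0.4 | 1.265 | 23.4% |
| 0.5 | 1.581 | 33.8% |

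The rows with d > 0 are not inflated type I error. If the list works, CBLI does differ from reflective writing, and a significant result is right about the contrast that was randomised. Nothing in the protocol supports a particular d for a handout seen in one session.

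**Review window.** Controls review 14 of 21 days (14/21 = 67%). The window from which CBLI meals are drawn is not stated in the text, and the meal-selection section and figure that it cites are not available. No difference between the arms can be shown.

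**Effect of matching the list.** If controls received it, meal selection and planning would still differ, so attribution to the thoughts alone would still fail.

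**The case for a change.** The strongest case for acting is that counterfactual thinking is the novelty the protocol claims under Innovation, so a positive trial will be read as evidence for it whatever the formal aim says. Control content is a design matter that no later analysis plan can repair. The remedy also looks cheap: hand controls the same list, or reword the aim and the expectation.

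Part of this stands. The contrast cannot credit the thoughts alone, and a report that did so would go beyond the design. The remedies are weaker than they look. Giving controls the list changes the comparator, is likely to shrink the contrast, may set controls thinking about alternatives, and still leaves the mechanism unidentified. Rewording alters no procedure, estimate or result. Stating whether controls receive the list would help a reader, but it only adds detail to a brief description; the protocol does not say that the list is withheld. Testing a whole intervention against an active control that shares the glucose and meal feedback, before taking it apart, is a fair choice for a study of at most 40 subjects.

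**Conclusion.** No change follows. The descriptions do differ, and the trial can support a conclusion about CBLI against reflective writing only, not about counterfactual thoughts in isolation. That limit belongs to interpretation. It does not bias the randomised comparison, and the protocol commits to no analysis or conclusion that oversteps it; the sentence that leans that way states an expectation. At most one clearly separable ingredient, the strategy list, is in question, and its absence from the control arm is inferred from silence. The 9% to 34% range rests wholly on assumed effects, an assumed equal split and an assumed test, and it describes true detections of a difference between the arms. The review window gives no evidence of imbalance. Matching the list across arms is an optional trade-off with costs on both sides. This judgement would change if a hypothesis or analysis elsewhere claimed to isolate counterfactual thinking from the rest of the session.
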